In an international research collaboration, we intend to translate and adapt hypnotherapy audio files — proven highly effective in a Dutch context — to Swedish conditions so that they can be used to treat children and adolescents in Sweden. The feasibility study described in this project plan is required to evaluate effect sizes and the practical aspects of the treatment. Our experience from previous treatment studies is that the insights gained from this type of feasibility study provide the knowledge needed to conduct large and successful randomized controlled trials (RCTs) in the next phase — for example, comparing hypnotherapy and iCBT in terms of effectiveness, cost-efficiency, and which patients respond best to which treatment. The overarching goal of the project is to help children and adolescents with FGID by ultimately introducing a new treatment option into standard care.

Feasibility Study Research Questions:

1. Can children and adolescents with pain-dominant FGID experience reduced gastrointestinal symptoms through hypnotherapy with audio files?
2. Can children and adolescents with pain-dominant FGID experience improved daily functioning through hypnotherapy with audio files?
3. Can children and adolescents with pain-dominant FGID experience improved quality of life through hypnotherapy with audio files?
4. What practical challenges may arise in patient recruitment, data collection, and the treatment itself (that need to be addressed before a larger RCT can be conducted)?

5. Feasibility Study Method:

A feasibility study of the hypnotherapy intervention without a control group to evaluate feasibility, acceptability, and effect sizes for the primary outcome measures.

Children (N=20–30) of school age (8–17 years) with pain-dominant FGID (defined according to the Rome IV criteria) will be recruited from a pediatric outpatient clinic in Stockholm. Measurements of, among other things, gastrointestinal symptoms, functional level, and quality of life will be conducted using validated instruments before, during (every three weeks), and after treatment.

6. Significance of the Feasibility Study:

The feasibility study will provide estimates of effect sizes for the outcome measures (required for power analysis) and offer invaluable practical experience that will make it possible to later carry out a successful large-scale clinical trial.

Project Description:

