The first part of the project (which this application concerns) consists of a feasibility study in which the applicability, preliminary effectiveness, and mechanisms of action of the hypnotherapy treatment will be evaluated in a smaller patient group. The goal is to recruit 20–30 patients with a confirmed FGID diagnosis from the pediatric gastroenterology clinic at Sachsska Children's Hospital and/or other hospital-based specialist clinics at Sachsska. These patients will undergo a 12-week treatment involving hypnotherapy self-exercises using audio files at least 5 times per week. Patients and their parents will complete self-report assessments on symptom severity, quality of life, school absenteeism, etc., using standardized questionnaires via an online platform every three weeks. A table listing the outcome measures is attached.

All patients will be contacted by a gastroenterology-focused physician or nurse at the clinic or by phone (if referred from another unit) before inclusion to assess inclusion and exclusion criteria, inform the family about the study, and go over the treatment principles.

Inclusion criteria:

- Age 8–17 years
- Confirmed diagnosis of functional dyspepsia, functional abdominal pain, or IBS according to Rome IV criteria (including evaluation for organic differential diagnoses)
- Reading and writing proficiency in Swedish
- Less than 40% school absenteeism
- Stable dose (for over 1 month) if on psychopharmacological medication

Exclusion criteria:

- Non-functional medical condition
- More than 40% school absenteeism
- Ongoing psychotherapeutic treatment
- Severe psychosocial or psychiatric problems requiring more intensive care than hypnotherapy

These criteria will be assessed using questionnaires and individual interviews before treatment begins.

Data Analysis:

For the feasibility study, 20–30 patients will be recruited — the number is based on prior experience with similar pilot studies. Data will be collected every three weeks from the start to the end of treatment via a secure online service with identity verification. The same platform will be used to distribute treatment files and instructions to patients and their parents. Data will be stored in a secure database protected by two-factor authentication and access control. Once the data is no longer needed for the study, the key to the code will be destroyed (no later than 10 years after data collection).

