1.1.1 Model specification

For each outcome variable with more than two measurements per patient (i.e., not only at week 0 and at week 12), we estimate the pre-post treatment effect using an LMM fitted by restricted maximum likelihood (REML). The model can be written as

$$y_{ij} = \beta_0 + \beta_1 \text{WEEK}_{ij} + u_i + \epsilon_{ij},$$

where y_{ij} represents the value of the outcome for patient i at week j , β_0 is the fixed intercept, β_1 is the fixed slope coefficient that captures the average change of the outcome variable given one more week of treatment, and u_i is the patient specific random intercept. By using random intercepts we allow patients to differ at baseline. For example, some patients might have much higher Peds-QL gastro than others at baseline.

Due to the small sample size the decision was made to not include quadratic effects or random slopes as it cause convergence issues. However, normally these should be included if they

improve the goodness of fit of the model (based on i.a. the distribution of residuals, likelihood ratio tests, or the Akaike information criterion). A model that includes both quadratic effects and random slopes can be written as

$$y_{ij} = \beta_0 + \beta_1 \text{WEEK}_{ij} + \beta_2 \text{WEEK}_{2ij} + u_{0i} + u_{1i} \text{WEEK}_{ij} + \epsilon_{ij} = \beta_0 + u_{0i} + (\beta_1 + u_{1i}) \text{WEEK}_{ij} + \beta_2 \text{WEEK}_{2ij} + \epsilon_{ij}.$$

By including a quadratic effect for weeks of treatment we account for nonlinear trends. For example, it might be that the effect of the treatment is decreasing over time. Furthermore, by including random slopes we allow for the weekly effect of the treatment to differ between patients.

For parent rated outcomes, we should also consider using a 3-level mixed model where we cluster the data by both parent and adolescent.

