1.1.2 LMM estimate of Cohen's d

To obtain a standardized pre-post treatment effect (Cohen's d), the LMM estimate of the 12-week treatment effect is divided (standardized) by the standard deviation at baseline. That is, the LMM estimate of Cohen's d is defined as

$$d = 12 \times \beta_1 \text{SD}_{\text{week}=0}.$$

The confidence interval for Cohen's d is based on the LMM estimated standard errors (SE), that is

$$SE_d = 12 \times SE_{\beta_1} \text{SD}_{\text{week}=0}.$$

Standard errors can also be computed using bootstrap. This is particularly useful in case of a complex model for which Cohen's d is estimated using more than one parameter. For example, if the model includes a quadratic treatment effect, then Cohen's d is estimated as follows

$$d = 12 \times \beta_1 + 12 \times \beta_2 \text{SD}_{\text{week}=0}.$$

The standard error of Cohen's d with a quadratic treatment effect can also be calculated using the formula $Var(aX+bY) = a^2 Var(X) + b^2 Var(Y) + 2abCov(X,Y)$, where $X = \beta_1$ and $Y = \beta_2$. However, since multicollinearity can be a problem in polynomial regression which can lead to inflated standard errors, the variable for weeks of treatment should first be centralized.

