1.5 Imputation of missing values

The pilot study includes 32 patients at baseline (week 0). Of these patients, there are 21 patients with complete follow-up (no missing data), 25 patients with no missing data at week 12, and 2 patients with no data after week 0. Data is rarely missing completely at random (MCAR). It is more likely to assume that there are systematic differences between the non-participating patients (i.e. the patients who at some point decided to drop out) and the participating patients, which could bias the results. For example, some patients might have discontinued the treatment due to insufficient treatment effect. If that is the case, there is a risk that the estimated effect of the treatment could be overestimated if the missing values are not handled correctly. For this reason, a sensitivity analysis was made, comparing the results of using no imputation to the results of using Last Observation Carried Forward (LOCF). A drawback of LOCF is that it underestimates the variability in the data, which can lead to too narrow confidence intervals. Another alternative is to use multiple imputation, which account for the uncertainty of estimating the missing data. However, if the observed data cannot account for the systematic differences, that is if the data is missing not at random (MNAR), multiple imputation may still lead to biased results.

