1.6 Limitations

No control group: It is important to note that since we do not have a control group to compare with, the risk of receiving biased results is high, especially due to the phenomenon known as regression toward the mean. That is, many of the patients who were in poor health at baseline (week 0) would probably have felt better at week 12 even without treatment.

No analysis of outliers: No analysis of outliers has been performed.

No comparison of models: Due to the small sample size, the decision was made to only fit an LMM with patient specific random intercepts. However, a larger sample size would enable us to use more complex models that can provide better fit to the data. In a more complex model we can for example include quadratic effects, random slopes, or interaction terms. For parent rated outcomes, we should also consider using a 3-level mixed model where we cluster the data by both parent and adolescent.

Modeling discrete variables as continuous variables: The outcome variable for pain frequency represents the number of days during a week that the individual felt pain, which means that it is a discrete variable with a minimum value of zero and a maximum value of seven. In this analysis we will model pain frequency as if it was a continuous variable using LMM for ease of interpretation. However, count data is usually modeled using Poisson regression.

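### For roughly normal outcomes the planned SE of the mixed-model Cohen's d is too small: it treats the baseline SD as known and counts only part of any between-patient slope variation

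*Combined protocol and SAP*

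**What the plan says.** Section 1.1.2 defines d as the estimated 12-week change, 12 × β1, which "is divided (standardized) by the standard deviation at baseline". (The fraction bar is lost in the extracted formula, but the sentence is clear.) The confidence interval "is based on the LMM estimated standard errors (SE), that is" 12 × SE(β1), scaled by the same baseline SD. No term allows for the SD being an estimate.

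The model behind SE(β1) is in section 1.1.1: a linear week effect with a random intercept per patient. The reason for going no further is given there: "Due to the small sample size the decision was made to not include quadratic effects or random slopes as it cause convergence issues". The section adds that such terms would normally be included if they improved fit.

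Section 1.1.2 also says "Standard errors can also be computed using bootstrap", chiefly with more complex models in mind. It gives no resampling unit, interval type, number of resamples or confidence level. For outcomes measured only at weeks 0 and 12, section 1.2 uses a paired d whose variance formula does contain a d²/2n term.

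**The concern.** An SE for d should reflect the sampling error of both the numerator and the denominator. Here the denominator is taken as fixed. The numerator's SE comes from a model in which every patient shares one slope. If patients improve at different rates, that model spreads the slope variation across visits as if it were independent noise, and so counts too little of it. Random slopes were dropped because of convergence, not because slopes were shown to be equal, and nothing in the plan says what this does to the interval.

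What is at stake is how precise the pilot's effect sizes appear. The item on the study's significance says "The feasibility study will provide estimates of effect sizes for the outcome measures (required for power analysis", and this interval is how the plan expresses their uncertainty. An interval that is too narrow invites too much trust in a single d when the next trial is sized.

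**Working it through.** **Inputs from the documents.** Section 1.5 gives 32 patients at baseline. The Data Analysis section says "Data will be collected every three weeks from the start to the end of treatment", and treatment lasts 12 weeks, so visits fall at weeks 0, 3, 6, 9 and 12. The within-patient sum of squares of week is then 36 + 9 + 0 + 9 + 36 = 90.

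**Assumptions.** The documents give no d, residual variance s², SD τ of patients' true 12-week changes, or confidence level, so there is no stated figure to reproduce. I take baseline SD = 1, s² = 0.4, a nominal 95% level, normal data and complete visits, and vary d and τ.

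**Formulas.**
- Since 144/90 = 1.6, equal slopes give Var(12β1) = 1.6 s²/n.
- With slope variation the true variance is (1.6 s² + τ²)/n. The random-intercept residual variance spreads the extra sum of squares over four within-patient degrees of freedom, so the model reports (1.6 s² + 0.25 τ²)/n.
- By the delta method, estimating the SD adds about d²/(2(n−1)) = d²/62. For normal data the covariance between the slope estimate and the baseline SD is zero.

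**Example without slope variation (τ = 0).** Planned variance = 1.6 × 0.4/32 = 0.0200, SE 0.141. At d = 0.5 the omitted term is 0.25/62 = 0.0040 (20%), and the interval is 0.22–0.78 instead of 0.20–0.80.

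**Example with slope variation (d = 0.8, τ = 0.5).** Planned variance = (0.64 + 0.0625)/32 = 0.0220, SE 0.148. Full variance = (0.64 + 0.25)/32 + 0.64/62 = 0.0278 + 0.0103 = 0.0381, SE 0.195. The interval is 0.51–1.09 instead of 0.42–1.18.

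**Closed form and simulated coverage of the planned interval (20,000 runs each).**

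| τ | d | Planned SE | Full SE | Ratio | Coverage |
|---|---|---|---|---|---|
| 0 | 0 | 0.141 | 0.141 | 1.00 | 94.7% |
| 0.3 | 0 | 0.144 | 0.151 | 1.05 | 93.4% |
| 0.5 | 0 | 0.148 | 0.167 | 1.13 | 91.3% |
| 0 | 0.3 | 0.141 | 0.146 | 1.04 | 94.0% |
| 0 | 0.5 | 0.141 | 0.155 | 1.10 | 92.4% |
| 0.3 | 0.3 | 0.144 | 0.156 | 1.08 | 92.9% |
| 0.3 | 0.5 | 0.144 | 0.164 | 1.14 | 91.2% |
| 0 | 0.8 | 0.141 | 0.174 | 1.23 | 88.5% |
| 0.5 | 0.8 | 0.148 | 0.195 | 1.32 | 85.7% |
| 0.8 | 0.8 | 0.158 | 0.224 | 1.42 | 82.9% |

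The simulated ratios of true to reported SE are slightly above the first-order formula: 1.05–1.16 for d 0.3–0.5 with τ 0–0.3, and 1.26–1.35 for d = 0.8 with τ 0–0.5.

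**Sensitivity of planned coverage.** The first figure is for d 0.3–0.5 with τ 0–0.3, the second for d = 0.8 with τ 0–0.5.
- s² of 0.3–0.5: 90–94% and 83–90%.
- s² of 0.6–0.7: 92–94% and 89–92%.
- Missing data as in section 1.5 ("there are 21 patients with complete follow-up (no missing data), 25 patients with no missing data at week 12", and two with baseline only), assuming which visits are missed and drop-out unrelated to outcome: 91.5–94.5% and 86.5–89.3%.

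**Other distributions.**
- Pain days, of which section 1.6 says "it is a discrete variable with a minimum value of zero and a maximum value of seven", simulated as binomial counts with |d| 0.5–0.9: 85–92%.
- Skewed gamma scores improving proportionally, coefficient of variation 0.68: 97%, 96%, 94% and 89% at |d| = 0.29, 0.44, 0.59 and 0.74. At the smaller effects the planned interval is, if anything, too wide.
- The same with coefficient of variation 0.45: 95.4%, 92.7%, 87.0% and 79.5% at |d| = 0.45, 0.67, 0.89 and 1.11.

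**The case against.** The strongest reply concerns materiality. At d = 0.5 with equal slopes each limit moves by about 0.02, which would change no conclusion in a single-arm pilot. No decision rule uses the interval. The point estimate carried into a power calculation is unchanged, and an uncontrolled pre-post d is not the effect on which a comparison with iCBT would be powered. Section 1.6 already names the missing control group and regression toward the mean, which a wider interval does not address. All of this stands, and it is why the point is minor.

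The size also rests on assumed inputs, and the slope component is hypothetical: it vanishes at τ = 0, and sections 1.1.1 and 1.6 disclose the simpler model. That stands too, but neither section mentions the effect on the SE. With τ = 0 the baseline-SD component alone brings coverage to 88.5% at d = 0.8.

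The documents do not show that any outcome is roughly normal, and for skewed scores the direction can reverse. The conclusion is therefore limited to roughly normal outcomes, although the simulated 0–7 counts also under-cover. The contrast with section 1.2 is only supporting evidence, because the paired d is a different estimator with a different standardiser.

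Finally, a bootstrap is already permitted. But it is optional and unspecified, and the unspecified choices matter. Resampling from the fitted random-intercept model still gave 92.3% at d = 0.8, τ = 0.5. Percentile intervals from resampled patients gave 88.1–94.1%.

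**Conclusion.** The concern holds. As written, the SE omits about d²/(2(n−1)) and three quarters of any between-patient variance in 12-week change. For normal data it is right only when d = 0 and all patients share one slope; otherwise it is too small. Under the stated assumptions the shortfall is minor at d 0.3–0.5 (coverage 91–94%) and worth correcting near d = 0.8 or above (86–89%). Coverage of 80–88% at d 0.3–0.8 needs strongly differing slopes (τ = 0.8, s² 0.3–0.5) and is the least expected case. The direction is firm for roughly normal outcomes. The size depends on d, s² and τ, which the documents do not give.

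**What to change.** Keep the random-intercept point estimate. In section 1.1.2, make a patient-level bootstrap the primary SE for the mixed-model d:

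- resample whole patients, entering a patient drawn twice as two separate patients;
- refit the model and recompute the baseline SD in each resample;
- report d ± 1.96 × bootstrap SE, and state the confidence level and number of resamples (999 was used in the runs below).

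A t quantile is acceptable but slightly wide. Avoid the plain percentile interval and resampling from the fitted random-intercept model. A closed form (patient-clustered CR2 variance plus d²/(2(n−1)), with a t quantile) can serve as a check for roughly normal outcomes. It is too wide for skewed ones (97.5–98.8% for the gamma scores).

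With complete data the recommended interval covered 94.7–95.7% for normal data, 93.2–95.9% for gamma scores and 95.0–95.4% for counts. With the missing-data counts of section 1.5 the figures were 95.1–96.1%, 94.7–95.8% and 94.9–95.6%. Those runs assume drop-out unrelated to outcome. Section 1.5 expects systematic drop-out, and the bootstrap does not remove bias from that.

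The cost is SAP wording and a few minutes of computing, with no new data. Relative to the planned SE with complete data, the bootstrap SE is 3% larger at d = 0, τ = 0; 8–18% larger at d 0.3–0.5, τ 0–0.3; 28–37% larger at d = 0.8, τ 0–0.5; and 17–43% larger for the simulated pain-day counts. For the gamma scores with coefficient of variation 0.68 it ranges from 4% smaller to 15% larger, so it also narrows the interval where the planned one is too wide.

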1.2 Cohen's d for paired data

Since the outcome variables for depression (CDI-S), anxiety (SCAS-S-C), quality of life of parents, and school absence only have two measurements per patient at week 0 and week 12, the decision was made to estimate the effect size for these variables using Cohen's adjusted d for paired data together with Hedges' small-sample bias correction, see Borenstein et al. (2009). It is important to note that as this estimator requires paired data only patients with an observed value at both week 0 and at week 12 can be included.

We let $(y_{i, \text{week}=0}, y_{i, \text{week}=12})$ denote a pair of observed values for some outcome variable Y at week 0 and 12 for patient i among n pairs with $d_i = y_{i, \text{week}=0} - y_{i, \text{week}=12}$. Then Cohen's d is defined as

$$d = \bar{Y}_{\text{diff}} \text{diff} S_{\text{within}} = \bar{Y}_{\text{diff}} \text{diff} / 2(1-r) \sqrt{}$$

where \bar{Y}_{diff} and S_{diff} is the mean and standard deviation of d_i , and r is the estimated correlation between weeks 0 and 12. The variance of Cohen's d is given by

$$V_d = (1/n + d^2/2n) 2(1-r).$$

To get the Hedges' corrected d , denoted g , we use the correction factor J as follows

$$g = J \times d V_g = J_2 \times V_d$$

where

$$J=1-34df-1$$

with the degrees of freedom $df=2n-2$.

1.3 Paired T-test

The paired T -test can be used to test the null hypothesis that the pre-post mean difference is equal to zero. The test requires paired data and shares strong similarities with Cohen's adjusted d for paired data. Letting \bar{Y}_{diff} denote the mean difference and S_{diff} denote the standard deviation of the difference, the test statistic is defined as

$$t=\bar{Y}_{diff}S_{diff}/n\sqrt{.}$$

1.4 Unpaired Two-sample T-test

To compare the effect of the hypnotherapy treatment between two age groups at week 12 we can perform a two-sample T-test assuming unequal variances. The test statistic is calculated as

$$t=\bar{y}_1-\bar{y}_2\sqrt{\frac{1}{s_{21}^2n_1+s_{22}^2n_2}}$$

where \bar{y}_1 and \bar{y}_2 represent the mean values, s_{21} and s_{22} represent the estimated variances, and n_1 and n_2 the sample sizes for age group 1 and 2 at week 12. Note that the T-test only uses data at week 12. Another option is to include an interaction term between age group and weeks of treatment in the mixed model in order to compare the pre-post treatment effect between the groups.

Seeing that our sample size is very small, we should avoid making too many tests as it could be viewed as P-value hacking.

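### The optional age-group t-test compares week-12 levels, so it measures a difference in treatment effect (pre-post change) only if the age groups start equal

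*Combined protocol and SAP*

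**What the plan says.** Section 1.4 of the SAP introduces an unequal-variance comparison of two age groups: "To compare the effect of the hypnotherapy treatment between two age groups at week 12 we can perform a two-sample T-test". It adds: "Note that the T-test only uses data at week 12". As an alternative it mentions an age group by week interaction in the mixed model, which would compare pre-post effects. It does not choose between the two, and it closes by advising against running many tests in so small a sample.

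Elsewhere the plan's effect is a change over time. In Section 1.1.2, "the LMM estimate of the 12-week treatment effect is divided (standardized) by the standard deviation at baseline". Section 1.2 works with paired week 0 minus week 12 differences. Section 1.3 uses the paired test to "test the null hypothesis that the pre-post mean difference is equal to zero".

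Section 1.6 says that, because the sample is small, only a random-intercept model is fitted, and it describes what a larger sample would allow: "In a more complex model we can for example include quadratic effects, random slopes, or interaction terms". The documents give no age cut-point, no age-group sizes and no baseline values by age.

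**The concern.** The stated purpose and the statistic do not match. A comparison of week-12 means asks whether older and younger children end at different levels. The purpose given is to ask whether they respond differently. The two questions coincide only when the groups have the same mean at week 0. Age is a patient characteristic and is not randomised, and Section 1.1.1 expects patients to differ at baseline.

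Two errors are possible. A difference in level that was there from the start could be reported as a difference in treatment effect, or a real difference in change could be cancelled by an opposite baseline gap and missed. The test also discards every visit before week 12. Because Section 1.4 asks for few tests, the one that is run should answer the question it is given.

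**Working it through.** The plan states no power or error rate for this test, so there is no figure of its own to reproduce.

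**Inputs from the documents**
- 32 patients at baseline, 25 with week-12 data, 21 complete, 2 with nothing after week 0 (Section 1.5).
- Ages 8 to 17 (Inclusion criteria).

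**Assumptions, not in the documents**
- Two-sided 5% level.
- SD of 1 at both weeks.
- The 25 patients split 12/13 or 8/17.
- Baseline gaps of 0 to 0.8 SD.
- Week 0 to week 12 correlation r of 0.4 to 0.8.

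**Step 1: what the test estimates.** For groups A and B,

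mean week-12 difference = (baseline A − baseline B) + (change A − change B).

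If the changes are identical, the second bracket is zero and the test measures the baseline gap alone. The equal-start condition applies to the patients analysed at week 12, not only to all those enrolled. Week-12 data are missing for 32 − 25 = 7 patients.

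**Step 2: rejection rate when the true changes are identical and the gap persists in full.** The noncentrality is gap / √(1/n₁ + 1/n₂). For 12/13, √(1/12 + 1/13) = 0.400, so a gap of 0.5 SD gives 0.5 / 0.400 = 1.25 on 23 degrees of freedom, and a rejection probability of 0.224. Simulating the Welch test (20,000 runs per scenario, r = 0.6) gives:

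| Baseline gap (SD) | Week-12 test, 12/13 | Change scores, 12/13 | Week-12 test, 8/17 | Change scores, 8/17 |
|---|---|---|---|---|
| 0 | 0.048 | 0.052 | 0.049 | 0.050 |
| 0.3 | 0.111 | 0.052 | 0.100 | 0.049 |
| 0.5 | 0.222 | 0.048 | 0.195 | 0.052 |
| 0.8 | 0.480 | 0.050 | 0.413 | 0.051 |

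The noncentral-t values for 12/13 (0.050, 0.111, 0.224, 0.482) agree. For 8/17 the pooled-variance formula gives 0.201 and 0.432 at gaps of 0.5 and 0.8, slightly above the Welch simulation. The week-12 rates do not depend on r: runs at 0.4 and 0.8 match to within 0.01.

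**Step 3: masking.** Take a true difference in change of +0.5 SD and a baseline gap of −0.5 SD, split 12/13. The expected week-12 difference is −0.5 + 0.5 = 0, and the week-12 test rejects about 5% of the time. The SD of a change score is √(2(1 − r)), which is 1.10, 0.89 and 0.63 at r = 0.4, 0.6 and 0.8. Comparing changes rejects in 19%, 27% and 47% of studies.

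**Step 4: where comparing changes also fails.** Suppose half of a 0.5 SD gap fades by week 12 for reasons other than treatment. The week-12 difference is then 0.25 SD and the difference in change is −0.25 SD. The rejection rates are 9% (week-12 test) and 10% (change scores), so neither comparison is causal.

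**Step 5: how the interaction should be tested.** The setting was 32 patients, weeks 0, 3, 6, 9 and 12, no missing visits, intercept variance 0.6, residual variance 0.4, no true age difference, and splits 16/16, 12/20 and 8/24.
- Standard errors from the random-intercept model reject about 5%, 8% and 15% of the time when the SD of individual 12-week change is 0, 0.5 and 1.0.
- Uncorrected patient-clustered standard errors reject 6.6% to 9.0%.
- A Welch test on per-patient slopes rejects 4.8% to 5.5%. With visits missing roughly as in Section 1.5 it rejects 4% to 5%.

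**The case against.** The strongest reply is that Section 1.4 already discloses that the test uses week 12 only, and in the same paragraph attaches the pre-post wording to the interaction. On that reading the fault is a loose word in an opening clause of an optional analysis that serves none of the four research questions, in a single-arm feasibility study that already warns of bias. The rejection rates also rest on assumed baseline gaps.

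Much of this stands. The reach is small, and the algebra is certain while the practical size is not. But naming the data used is not the same as stating the equal-start condition, and the result would still be labelled a comparison of effect. Section 1.6 also leans towards the interaction not being fitted, which would leave the week-12 test as the one that runs.

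Three objections to the remedy also stand in part.
- Comparing changes is open to regression to the mean (Step 4).
- It can cost power. With a true difference of 0.8 SD, no baseline gap and a 12/13 split, it rejects about 37%, 48% and 69% of the time at r = 0.3, 0.5 and 0.7, against 48% for the week-12 test.
- Section 1.5 suggests the data are already in hand, so an outcome and cut-point chosen now would be post hoc.

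These limit what can be claimed. They do not make a week-12 level a measure of effect.

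**Conclusion.** The concern holds and should be fixed, with limited reach. That the week-12 difference mixes the baseline gap with the difference in change is an identity and needs no assumption. Its size does: with gaps of 0.3 to 0.8 SD that persist in full and identical true change, the week-12 test rejects in about 11% to 48% of studies (12/13) or 10% to 41% (8/17), instead of 5%. A gap of 0.5 SD in the opposite direction can hide a true difference in change of the same size. The actual gap between age groups is unknown. Sections 1.4 and 1.6 together do not settle whether the interaction will be fitted. The main pre-post estimates are unaffected.

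**What to change.** - In Section 1.4, drop the week-12 t-test or describe it as a comparison of week-12 levels.
- Make the age group by week comparison the single age-group analysis, and state its outcome and age cut-point. If the data have been seen, label these choices post hoc.
- Use inference that allows patients to differ in their change and suits a small sample. A Welch test on per-patient slopes does this, using at most 32 − 2 = 30 patients. Clustered standard errors with a small-sample correction are another choice, though only the uncorrected form was checked here.
- For outcomes measured only at weeks 0 and 12, apply a Welch test to individual changes.
- Reconcile the statement on interaction terms in Section 1.6 with this choice.
- Report the estimate with a confidence interval as a difference in change by age. Without a control group it is not a causal difference in effect.

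The cost is short edits to two sections and a little more analysis, with no new data. The estimate will be imprecise. At 16/16 with complete visits, the 95% interval half-width for the difference in 12-week change is 0.57, 0.68 and 0.92 SD when the SD of individual change is 0, 0.5 and 1.0. With visits missing roughly as in Section 1.5 it is about 0.8 to 1.3 SD.

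### The optional age comparison in section 1.4 uses two age groups with no stated cut-point; one exploratory analysis of age in years would be better

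*Combined protocol and SAP*

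**What the plan says.** The inclusion criteria admit children aged 8 to 17, which is ten year-values. Section 1.4 then offers a Welch test: "To compare the effect of the hypnotherapy treatment between two age groups at week 12 we can perform a two-sample T-test". It adds an alternative: "Another option is to include an interaction term between age group and weeks of treatment in the mixed model". Both routes reduce age to two groups. No section defines the groups, and none proposes age in years.

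The same section cautions that "we should avoid making too many tests as it could be viewed as P-value hacking", but sets no limit on the number of tests and no rule for forming the groups.

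Three other places bear on the point:

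- Section 1.5 reports 32 patients at baseline, "25 patients with no missing data at week 12", and 2 patients with nothing after week 0. It describes a sensitivity analysis in the past tense.
- Section 1.1.1 excludes random slopes because of convergence problems.
- Section 1.6 says only a random-intercept model is fitted, and leaves interaction terms to a larger sample.

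**The concern.** Two separate weaknesses follow from the undefined split.

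First, cutting a measured variable into two groups treats an 8-year-old and a 12-year-old as the same, and a 12- and a 13-year-old as different. With about 25 children at week 12, the information lost is hard to spare. The loss occurs whether week-12 scores or changes are compared.

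Second, a cut that is not written down can be chosen once results are visible. Each cut tried is a test, reported or not, so the plan leaves open the multiplicity that section 1.4 itself warns against. The study is meant to inform a later RCT, so a false age signal, or a missed one, could be carried forward.

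**Working it through.** The plan gives no cut-point, age distribution, significance level or power for this comparison, so there is no figure of its own to reproduce.

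**Inputs from the document.** Age 8–17 (inclusion criteria); Welch two-sample test (section 1.4); 25 patients at week 12 and 32 at baseline (section 1.5). The 32 would apply only if week-12 values were filled in, as LOCF would do.

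**Assumptions.** Whole-year ages spread evenly, a linear age trend unless stated otherwise, and a two-sided 5% level.

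**Step 1: information kept by a split.** Under a linear trend this is the squared correlation between age and the group indicator, cov² / [var(age) × q(1 − q)], where q is the share in the older group. For ages 8 to 17 the variance is (10² − 1)/12 = 8.25. For older group = 13 and over, q = 0.5 and the covariance is 0.5 × 0.5 × (15 − 10) = 1.25, because the group means are 15 and 10. So the share kept is 1.25² / (8.25 × 0.25) = 1.5625 / 2.0625 = 0.758, a loss of 24.2%.

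| Older group starts at | Information lost |
|---|---|
| 13 | 24% |
| 12 or 14 | 27% |
| 11 or 15 | 36% |
| 10 or 16 | 52% |
| 9 or 17 | 73% |

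**Step 2: sensitivity to the age distribution.** The loss at the best cut is 31.6% for a triangular distribution, 26.8% to 27.6% for two distributions skewed to older ages, 36.3% for normal ages cut at the median, and 13.4% for a bimodal distribution.

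**Step 3: power at n = 25** (simulation, 8,000 data sets per scenario).

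| True trend | Correlation | Age in years | Split at 13 |
|---|---|---|---|
| Linear | 0.5 | about 75% | about 60% |
| Linear | 0.4 | about 54% | about 42% |
| Linear | 0.2 | about 16% | about 13% |
| Step at 13 | 0.5 | about 62% | about 76% |
| Step at 13 | 0.4 | about 42% | about 52% |

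**Step 4: false positives with no true age effect** (simulation, 100,000 data sets for each n).

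| How the cut is chosen | n = 25 | n = 32 |
|---|---|---|
| One cut fixed in advance, 11 to 15 | 4.9–5.4% | 5.0–5.1% |
| Smallest p over cuts 12, 13, 14 | 10.1% | 10.1% |
| Smallest p over all cuts with at least 5 per group | 17.5% | 20.0% |
| Smallest p over all nine cuts | 28.6% | 28.6% |

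A single pre-set cut at 10 or 16 gives about 6%, and at 9 or 17 about 8–9%, because one group is then very small.

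**Step 5: is an age-by-WEEK term a safe replacement?** Assume 32 − 2 = 30 patients with follow-up, five visits, between-patient SD 1, residual SD 0.6 and no true age effect. In the random-intercept-only model the false-positive rate is about 10% if true 12-week changes vary between patients with SD 0.6, and about 15% at SD 0.96. Regressing each patient's own slope on age stays at about 5%. The model's standard error is too small because it leaves out variation in slopes.

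**The case against.** The strongest reply is that this is an optional, exploratory comparison in an uncontrolled feasibility study. The wording is permissive, none of the research questions concerns age, and the question of who responds best is left to the later RCT. No section says that an age result will set the RCT's age range or stratification. All of this stands, and it limits the severity.

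A second reply is that the advantage of age in years depends on a linear trend. That also stands: a step at 13 reverses the power ranking, and a scatter plot of 25 children is only a weak check of shape. At a correlation of 0.2 neither analysis is informative.

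A third reply is that replacing age group by age in the mixed-model interaction would add a term that section 1.6 defers, and would give false positives when slopes differ. Step 5 bears this out, so the remedy must avoid that model.

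Three stronger readings are tempting and are not supported:

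- A reader might infer that at least a quarter of the information must be lost. The document gives no age distribution, even ages give 24.2%, and a bimodal distribution would lose about 13%.
- A reader might infer that the error rate depends on where the cut lies. For a pre-set cut with reasonable group sizes it stays near 5%; the inflation comes from choosing the cut after seeing results.
- A reader might infer that several cuts were or will be tried. Nothing in the document says so; it only leaves this open.

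**Conclusion.** The point holds as a minor one. The two age groups are undefined in a plan written when follow-up data existed, and both options in section 1.4 discard information about age. Under even ages and a linear trend the cost is about 24% of the age information at the best cut, and roughly 15 percentage points of power at n = 25 and correlation 0.5. The 10% to 20% error rates apply only if the cut is picked after seeing results, and measure what the present wording permits. The correlations, the 5% level and the age distribution are assumptions, since the document gives none of them.

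**What to change.** Replace the two-group comparison in section 1.4 with one analysis, labelled exploratory, of centred age in years on a single named outcome:

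- for a two-visit outcome, regress each patient's week 0 to week 12 change on age;
- for a repeated outcome, estimate each patient's own slope over the weeks and regress those slopes on age.

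Report the effect per year of age with its confidence interval and a scatter plot. Do not use age-by-WEEK in the random-intercept-only model. Naming one outcome keeps the change in line with the section's own caution on the number of tests. It also makes the comparison one of change, whereas section 1.4 concedes of its test: "Note that the T-test only uses data at week 12".

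If groups are kept for a clinical reason, state one cut, the reason for it, and whether it was fixed before outcomes were seen.

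The cost is SAP wording only; no new data are needed. The downside is the assumption of a roughly linear age trend, with less power than a split if the true effect is a step at the chosen age.
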